11.5. Pharmacokinetic Analyses

Study drug concentration data will be listed by dose cohort/arm and summarized at each time point using descriptive statistics (arithmetic mean, standard deviation [SD], coefficient of variation, geometric mean, median, minimum, and maximum). All concentrations below the lowest quantifiable concentration or missing data will be labeled as such in the concentration data presentation. Concentrations below the lowest quantifiable concentration will be treated as zero in the summary statistics and for the calculation of PK parameters. All subjects and samples excluded from the analysis will be clearly documented in the study report.

Subjects will be excluded from the PK analysis if their data do not allow for accurate assessment of the PK (eg, incomplete administration of the study agent, concentration data not sufficient for PK parameter calculation due to missing PK draws at multiple visits, or early discontinuation from the study). The data from both phases of the studies will also be analyzed using population PK analysis via nonlinear mixed-effect modeling. Previously developed PK models may be used and updated as considered appropriate. Data may be combined with data from other studies to support a relevant structural population-based PK model. Available subject characteristics (demographics, laboratory variables, genotypes, etc.) may be tested as potential covariates affecting PK parameters. Individual PK parameters and metrics of exposure for erdafitinib, cetrelimab, and carboplatin/cisplatin will be summarized. Details of population PK analyses will be provided in a separate analysis plan and results will be described in a separate report, if such analyses are performed.

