11.1.1. Sample Size - Phase 1b

The total number of subjects to be enrolled in Phase 1b will depend on the dose level at which DLT of the combination are met or the RP2D is determined. Once a dose level is opened for enrollment, subjects will be entered in groups of 3 unless otherwise clinically indicated. A minimum of 6 subjects will be treated at a dose level or at the next higher level before the dose level can be declared as the RP2D. The expected number of subjects to be enrolled in the Phase 1b erdafitinib + cetrelimab cohort is 12 to 30.

A total of approximately 40 subjects will be enrolled in the Phase 1b erdafitinib + cetrelimab + platinum (cisplatin or carboplatin) chemotherapy cohort. Three subjects (either wild-type or with select FGFR gene alterations) will be enrolled in the initial erdafitinib + cetrelimab + cisplatin dose level (50 mg/m^2). If the starting dose is safe, 6 additional subjects will be enrolled into the escalated dose of cisplatin (60 mg/m^2). Out of 6 subjects, up to 3 subjects can be wild-type and the other subjects should be with select FGFR gene alterations. Wild-type is defined as subjects without FGFR gene alteration and subjects with FGFR gene alterations other than the select FGFR alterations as described in Table 4. Approximately 10 additional subjects with select FGFR gene alterations will be enrolled at the MTD for erdafitinib + cetrelimab + cisplatin.

Three subjects (either wild-type or with select FGFR gene alterations) will be enrolled in the initial erdafitinib + cetrelimab + carboplatin dose level ($\text{AUC}4 \text{ mg/mL/min}$). If the starting dose is safe, 6 additional subjects will be enrolled into the escalated dose of carboplatin ($\text{AUC}5 \text{ mg/mL/min}$). Out of 6 subjects, up to 3 subjects can be wild-type and the other subjects should be with select FGFR gene alterations. Approximately 10 additional subjects with select FGFR gene alterations will be enrolled at the MTD for erdafitinib + cetrelimab + carboplatin.

11.1.2. Sample Size - Phase 2

In Phase 2, approximately 90 subjects will be assigned randomly in a 1:1 ratio to receive either erdafitinib monotherapy treatment (Arm A) or erdafitinib and cetrelimab combination therapy (Arm B).

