^g Optional paired biopsies will be collected in the Phase 1b erdafitinib + cetrelimab + platinum-based chemotherapy cohort. An additional optional biopsy will be collected upon PD.

^h C4D1: Pre-infusion and EOI, C4D8: Post start of infusion, C4D15: Post start of infusion, and C5D1: Pre-infusion and EOI.

ⁱ For **Cisplatin**: PK samples are to be collected from the arm opposite from infusion site. If drug was administered via a central venous catheter, sample collection for PK should be from a different site.

Cisplatin PK sample to be drawn at C1D1: Pre-infusion, EOI (within 5 min), 2h (±10 min), 4h (±10 min), and 8h (±10 min); C2D1 and C3D1: Pre-infusion; C4D1: Pre-infusion, EOI (within 5 min), 1.5h (±10 min), 2h (±10 min), 4h (±10 min), 8h (±10 min); and at any unscheduled visit(s). Sampling times are relative to the beginning of the infusion. Pre-infusion samples should be drawn within 30 minutes before the infusion begins. Cisplatin is planned to be infused over 1 to 2h. If infusion duration is 1.75 to 2h, then the 2h PK sample can be eliminated as EOI would cover this 2h timepoint.

^j For **Carboplatin**: PK samples are to be collected from the arm opposite from infusion site. If drug was administered via a central venous catheter, sample collection for PK should be from a different site

Carboplatin PK sample to be drawn at C1D1: Pre-infusion, EOI (within 5 min), 1h (±10 minutes), 2h (±10 minutes), 4h (±10 minutes), and 8h (±10 minutes); C2D1 and C3D1: Pre-infusion; C4D1: Pre-infusion, EOI (within 5 min), 1h (±10 minutes), 2h (±10 minutes), 4h (±10 minutes), and 8h (±10 minutes); and at any unscheduled visit(s). Sampling times are relative to the beginning of the infusion. Pre-infusion samples should be drawn within 30 minutes before the infusion begins. Carboplatin is planned to be infused over 15 to 60 mins. If infusion duration is 45 to 60 min, then the 1h PK sample can be eliminated as EOI would cover this 1h timepoint.

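### Protocol Section 11.5 reports geometric means of concentration but sets unquantifiable values to zero without exception, so any time point mixing measurable and unmeasurable values has a geometric mean of 0 or undefined

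*Protocol*

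**What the plan says.** Protocol Section 11.5 (Pharmacokinetic Analyses) says that study drug concentrations will be "summarized at each time point using descriptive statistics (arithmetic mean, standard deviation [SD], coefficient of variation, geometric mean, median, minimum, and maximum". It then gives a display rule: "All concentrations below the lowest quantifiable concentration or missing data will be labeled as such in the concentration data presentation". The calculation rule follows: "Concentrations below the lowest quantifiable concentration will be treated as zero in the summary statistics and for the calculation of PK parameters".

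The display rule governs how such values are shown and leaves the calculation rule as it stands. Section 11.5 does not exempt the geometric mean from the zero rule, by exclusion, by another substitution or by a not-calculable convention. The only further plan that Section 11.5 names is the one for population pharmacokinetics. Section 11 says in general that specific details will be in the statistical analysis plan, which was not available for this review.

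**The concern.** Two instructions in one section cannot both be carried out. A geometric mean is required at each time point, and values on which it cannot be computed are required to enter it. This is a rule that the protocol itself fixes and that fails when followed, so it is more than a detail left open. An analysis plan could repair it only by departing from the protocol's unqualified sentence.

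Concentrations and pharmacokinetic parameters are a secondary endpoint in both Phase 1b cohorts (Appendices 1 and 2, Section 2.1), and concentrations are one in Phase 2 (Appendix 3, Section 2.1). Section 3.2 also gives weight to the platinum pharmacokinetic evaluation because of the drugs' narrow therapeutic range. If the rule is left alone, a programmer will have to improvise, and the convention chosen could differ between tables without being documented.

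**Working it through.** The protocol states no figure on this point, so there is none to reproduce. The check has three steps.

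**1. The arithmetic of one zero.** The geometric mean is (x₁ × … × xₙ)^(1/n), or equally exp[(1/n) Σ ln xᵢ].

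- Illustrative values 40, 45, 50, 55: product 4,950,000; fourth root 47.2.
- Add one value set to 0: the product form gives 0. The log form needs ln(0), which is minus infinity, so the result is 0 or undefined.
- The arithmetic mean of the five values is (40 + 45 + 50 + 55 + 0)/5 = 38.0, which is computable.

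The result does not depend on n. In simulated sets (an assumption: lognormal, median 100, log-SD 0.4) with one value below quantification:

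| n | No value below | Section 11.5 rule | Value left out | Half the limit (limit 1) | Half the limit (limit 10) |
|---|---|---|---|---|---|
| 6 | 110.9 | 0 | 110.1 | 44.8 | 65.8 |
| 10 | 102.0 | 0 | 104.7 | 61.4 | 77.2 |
| 45 | 95.7 | 0 | 95.6 | 85.1 | 89.5 |

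The quantification limits are assumed; the protocol gives none. The table also shows that at small n the answer depends heavily on the convention, so the convention has to be written down.

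**2. How often one such value would occur.** The chance of at least one in n samples is 1 − (1 − p)ⁿ. For assumed per-sample rates p of 1% to 10%, this is 6% to 47% at n = 6, 10% to 65% at n = 10, and 36% to 99% at n = 45. The last n is roughly one Phase 2 arm (Section 11.1.2: "In Phase 2, approximately 90 subjects will be assigned randomly in a 1:1 ratio"); end-of-treatment and follow-up samples would be fewer.

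**3. Where mixing is plausible.**

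- *Cisplatin, late post-dose.* Section 1.6 gives a plasma half-life of about 0.5 h. Appendix 2 Table 2 schedules an 8 h sample at C1D1 and C4D1, timed from the start of a 1 to 2 h infusion. That is 8 − 2 = 6 h to 8 − 1 = 7 h after the end, or 12 to 14 half-lives. The fraction remaining is 2⁻¹² ≈ 0.02% to 2⁻¹⁴ ≈ 0.006%. This assumes that the assay measures the species with that half-life. Whether the samples then mix or are nearly all unmeasurable depends on the limit, which is not stated.
- *Cetrelimab, end of treatment and first follow-up.* The sampling tables in Appendices 1 to 3 take these samples at any time during the end-of-treatment visit and, if possible, at the first follow-up visit, so time since last dose varies. The protocol gives no figure from which to quantify the mixing.
- *First pre-dose sample.* All values should be below quantification. A geometric mean of 0 does no harm there, although the coefficient of variation becomes 0/0.
- *Carboplatin before C2D1 and C3D1.* With the longest half-life in Section 1.6, 5.9 h, 21 days is 21 × 24/5.9 = 85 half-lives. Values should be almost uniformly unmeasurable, and zero is a fair summary.
- *On-treatment erdafitinib and cetrelimab troughs.* Erdafitinib is given daily with a half-life above 50 h and 3- to 5-fold accumulation (Section 1.3). Cetrelimab medians are 44.8 µg/mL before the fifth dose at 240 mg Q2W and 30 µg/mL after the first 480 mg dose (Section 1.5.2). These should be well above zero.

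**The case against.** The strongest reply is that little harm follows. A geometric mean of 0 or a blank is a visible gap rather than a plausible but misleading estimate. The arithmetic mean, SD, median and range stand beside it, values below quantification are labelled, and table conventions of this kind usually sit in an analysis plan. No decision rule in the protocol uses a geometric mean. All of this stands and sets the weight of the point. It does not remove the conflict, because the protocol has already written the convention and the convention cannot be followed for one of the listed statistics.

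A reader might infer that trough and pre-infusion summaries in general would be wrong. The documents do not support that: the on-treatment troughs of the two main drugs should be measurable, and the first pre-dose and carboplatin pre-infusion samples should be nearly uniform zeros.

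A reader might also infer that pharmacokinetic parameters would be miscalculated, because the same sentence covers them and a log-linear terminal slope cannot use a zero. Section 11.5 names no terminal slope or half-life, and it plans population modelling under a separate analysis plan. If a slope were fitted, the zero would simply drop out, so no wrong parameter value is shown. A clarifying sentence is enough.

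It is also fair to object that computing the geometric mean on quantifiable values alone has its own defect. In the example it gives 47.2 beside an arithmetic mean of 38.0, although a geometric mean cannot exceed the arithmetic mean of the same data. The two figures rest on different denominators, and the first is biased upward. That objection is accepted, and the change proposed requires the separate denominator to be shown.

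**Conclusion.** The point holds within limits. Followed literally, Section 11.5 gives a geometric mean of 0 or undefined at any time point where measurable and unmeasurable values mix, at every sample size. The arithmetic rests on no assumption. How many time points are affected does: it depends on quantification limits and rates of unmeasurable values that the protocol does not give. The plausible places are late cisplatin post-dose samples and cetrelimab at end of treatment and first follow-up.

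The consequence is confined to descriptive pharmacokinetic tables. The response-rate, safety and dose-limiting toxicity analyses are unaffected. The change is desirable, and it is not a condition for relying on the trial's main results.

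**What to change.** Amend Section 11.5, or state in the pharmacokinetic part of the analysis plan as an explicit departure from it:

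- The zero rule applies to the arithmetic mean, SD, coefficient of variation, median, minimum and maximum. The coefficient of variation is shown as not calculable where every value is below quantification.
- Zeros do not enter the geometric mean. Choose one of two conventions: report it as not calculable when any value is below quantification, or compute it on quantifiable values only. Under the second, print its own n and the number and percent below quantification beside it, with a note that it is biased upward and not comparable with the arithmetic mean.
- If any noncompartmental log-linear slope is fitted, values below quantification after the peak are treated as missing rather than zero.

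The cost is a few lines of text and one added row in the concentration tables. No sampling, sample size or study procedure changes.

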11.6. Immunogenicity Analyses

The incidence of antibodies to cetrelimab will be summarized for all subjects who receive a dose of cetrelimab and have appropriate samples for detection of antibodies to cetrelimab.

11.7. Pharmacodynamic Analyses, and Biomarker Analyses

CCI

over time will be summarized by treatment group. Associations between baseline levels and changes from baseline in selected markers and clinical response will be explored.

Results of exploratory pharmacodynamic biomarker analyses may be presented in a separate report. Planned biomarker analyses may be deferred or canceled if emerging data show no likelihood of providing useful scientific information.

11.8. Pharmacokinetic/Pharmacodynamic Analyses

Model-derived exposure parameters of erdafitinib, cetrelimab, and platinum chemotherapy may be used to explore PK/PD correlation for key efficacy and safety parameters, including the influence of covariates, and inter-individual variability between exposure with relevant clinical or biomarker information using a population PK/PD approach. Details of these population PK/PD analyses will be provided in a separate analysis plan and results may be described in a separate report.

11.9. Safety Analyses

Adverse Events

The verbatim terms used in the eCRF by investigators to identify AEs will be coded using the most current version of the Medical Dictionary for Regulatory Activities (MedDRA). Toxicities will be graded for severity according to NCI-CTCAE, version 5.0 (see [Table 7](#) for nail toxicity and hyperphosphatemia grading). All reported AEs with onset during the treatment period (ie, TEAEs and AEs that have worsened since baseline) will be included in the analysis.

Specifically, the following will be summarized:

- Incidence of DLT (Phase 1b)
- All AEs, including irAEs
- Grade 3 or higher AEs
- Serious AEs
- AEs leading to permanent discontinuation of treatment
- AEs leading to death

Summaries, listings, datasets, or subject narratives may be provided, as appropriate, for those subjects who die, who discontinue treatment due to an AE, or who experience a severe AE or an SAE.

Clinical Laboratory Tests

Laboratory data will be summarized by type of laboratory test. Reference ranges and markedly abnormal results (specified in the Statistical Analysis Plan) will be used in the summary of laboratory data. Descriptive statistics will be calculated for each laboratory analyte at baseline. Parameters with predefined toxicity grades will be summarized. Change from baseline to the worst Grade experienced by the subject during the study will be provided as shift tables.

Parameters with predefined NCI-CTCAE toxicity grades will be summarized. Change from baseline to the worst AE Grade experienced by the subject during the study will be provided as shift tables.

Vital Signs

Descriptive statistics of pulse/heart rate and blood pressure (systolic and diastolic), and change from baseline will be summarized at each scheduled time point. The percentage of subjects with values beyond clinically important limits will be summarized.

Physical Examination

Frequency tabulations of the abnormalities will be made.

Electrocardiogram

The effects of erdafitinib and cetrelimab on ECGs (QT, QTc, PR, QRS, heart rate) will be evaluated by means of descriptive statistics and frequency tabulations. These tables will include observed values and changes from baseline values to allow detection of clinically relevant changes in individuals.

11.10. Data Review Committee

A DRC will be established to monitor data on an ongoing basis to ensure the safety of the subjects enrolled in Phase 2 of this study. Additionally, the DRC may review ongoing cumulative data from Phase 1b after the RP2D has been determined.

The DRC will consist of at least 2 medical experts in the relevant therapeutic area and at least 1 statistician. The DRC responsibilities, authorities, and procedures will be documented in a separate DRC charter.

12. ADVERSE EVENT REPORTING

Timely, accurate, and complete reporting and analysis of safety information from clinical studies are crucial for the protection of subjects, investigators, and the sponsor, and are mandated by regulatory agencies worldwide. The sponsor has established Standard Operating Procedures in conformity with regulatory requirements worldwide to ensure appropriate reporting of safety information; all clinical studies conducted by the sponsor or its affiliates will be conducted in accordance with those procedures.

Method of Detecting Adverse Events and Serious Adverse Events

Care will be taken not to introduce bias when detecting AEs or SAEs. Open-ended and nonleading verbal questioning of the subject is the preferred method to inquire about AE occurrence. For some studies, subjects are not always able to provide valid verbal responses to open-ended questions. In these circumstances, the investigator will decide the appropriate method of reporting the AE.

Solicited Adverse Events

Solicited AEs are predefined local and systemic events for which the subject is specifically questioned.

Unsolicited Adverse Events

Unsolicited AEs are all AEs for which the subject is specifically not questioned.

12.1. Definitions

12.1.1. Adverse Event Definitions and Classifications

Adverse Event

An AE is any untoward medical occurrence in a clinical study subject administered a medicinal (investigational or non-investigational) product. An AE does not necessarily have a causal relationship with the treatment. An AE can therefore be any unfavorable and unintended sign (including an abnormal finding), symptom, or disease temporally associated with the use of a medicinal (investigational or non-investigational) product, whether or not related to that medicinal (investigational or non-investigational) product. (Definition per International Conference on Harmonisation [ICH]).

This includes any occurrence that is new in onset or aggravated in severity or frequency from the baseline condition, or abnormal results of diagnostic procedures, including laboratory test abnormalities.

Note: The sponsor collects AEs starting with the signing of the Full-Study ICF (refer to Section 12.3.1, All Adverse Events, for time of last AE recording).

Serious Adverse Event

An SAE based on ICH and European Union (EU) Guidelines on Pharmacovigilance for Medicinal Products for Human Use is any untoward medical occurrence that at any dose:

- Results in death
- Is life-threatening
(The subject was at risk of death at the time of the event. It does not refer to an event that hypothetically might have caused death if it were more severe)
- Requires inpatient hospitalization or prolongation of existing hospitalization
- Results in persistent or significant disability/incapacity
- Is a congenital anomaly/birth defect
- Is a suspected transmission of any infectious agent via a medicinal product
- Is Medically Important*

*Medical and scientific judgment should be exercised in deciding whether expedited reporting is also appropriate in other situations, such as important medical events that may not be immediately life-threatening or result in death or hospitalization but may jeopardize the subject or may require intervention to prevent 1 of the other outcomes listed in the definition above. These should usually be considered serious.

If a serious and unexpected AE occurs for which there is evidence suggesting a causal relationship between the study drug and the event (eg, death from anaphylaxis), the event must be reported as a serious and unexpected suspected adverse reaction even if it is a component of the study endpoint (eg, all-cause mortality).

Unlisted (Unexpected) Adverse Event/Reference Safety Information

An AE is considered unlisted if the nature or severity is not consistent with the applicable product reference safety information. For erdafitinib and cetrelimab, the expectedness of an AE will be determined by whether or not it is listed in the IB.

Adverse Event Associated With the Use of the Drug

An AE is considered associated with the use of the drug if the attribution is possible, probable, or very likely by the definitions listed in Section 12.1.2, Attribution Definitions.

12.1.2. Attribution Definitions**Not Related**

An AE that is not related to the use of the drug.

Doubtful

An AE for which an alternative explanation is more likely, eg, concomitant drug(s), concomitant disease(s), or the relationship in time suggests that a causal relationship is unlikely.

Possible

An AE that might be due to the use of the drug. An alternative explanation, eg, concomitant drug(s), concomitant disease(s), is inconclusive. The relationship in time is reasonable; therefore, the causal relationship cannot be excluded.

Probable

An AE that might be due to the use of the drug. The relationship in time is suggestive (eg, confirmed by dechallenge). An alternative explanation is less likely, eg, concomitant drug(s), concomitant disease(s).

Very Likely

An AE that is listed as a possible adverse reaction and cannot be reasonably explained by an alternative explanation, eg, concomitant drug(s), concomitant disease(s). The relationship in time is very suggestive (eg, it is confirmed by dechallenge and rechallenge).

